## 11.5.4.2. Secondary Efficacy/Pharmacodynamic Endpoints

For the secondary/PD endpoint, PLP change from Baseline to pre-3rd dose Week 9, similar methods as for PPi will be employed.

## 11.5.5. Statistical Methods: Pharmacokinetics Analysis

Following dosing at Week 1, Day1, mean serum asfotase alfa concentrations versus *nominal* time, and individual serum asfotase alfa concentrations versus *actual* time will be graphically presented for both linear and semi-log scales. The individual serum concentration data for patients in each cohort, with actual sampling dates and times will be used to derive the PK parameters by non-compartmental analyses using WinNonlin®5.3 (or higher) (Certara, L.P., [name]). The following PK parameters will be calculated and summary statistics reported by cohort and by patient:  $C_{max}$ ,  $t_{max}$ ,  $AUC_t$ ,  $AUC_\infty$ ,  $k_e$ , and  $t_{1/2}$ . Both the single-dose and multiple-dose PK will be characterized. Descriptive statistics (mean, SD, CV, median, minimum, maximum, geometric mean, and geometric %CV) of the serum concentration and PK parameters will be presented. An attainment of asfotase alfa PK steady state will be evaluated. Dose proportionality and time linearity assessment may be considered. Graphical displays of PK data will be presented as appropriate.

Relationships between PK and PD parameters may be explored if considered appropriate. The PK and PD data from this study may be combined with data from other studies.

## 11.5.6. Statistical Methods: Safety Variables

Summaries for all safety variables will be computed and displayed by cohort.

## 11.5.6.1. Safety Variable: Adverse Events

Safety assessments will be based on the incidence of AE reports. Adverse events will be coded using MedDRA and will be summarized by System Organ Class (SOC) and Preferred Term (PT). A detailed listing of patients who experience AEs and SAEs will be presented. Adverse event severity will be categorized as mild, moderate, or severe. The highest severity will be assigned to a patient should more than 1 occurrence of the same AE be reported with a different severity. Relationships of the AE to treatment will be categorized as not related/unrelated, unlikely related, possibly related, probably related, or definitely related. The highest level of association will be reported in patients with differing relationships for the same AE. A listing of AEs for all patients will be provided. A separate listing for patients who withdraw from the study due to AEs will be provided. The incidence of AEs will be tabulated by severity, and by relationship to treatment. The incidence of AEs leading to study discontinuation will also be summarized. Adverse events occurring on the day of infusion will be summarized, and a separate listing will be produced for these AEs. All summary tables and data listings of AEs will be presented by cohort.

#### 11.5.6.2. Safety Variable: Injection-Associated Reactions

Injection-associated reactions will be analyzed in the same manner as AEs.

## 11.5.6.3. Safety Variable: Injection Site Reactions

Injection site reactions will be analyzed in the same manner as AEs.

## 11.5.6.4. Safety Variable: Laboratory Tests Including Clinical Hematology, Chemistry, and Urinalysis

Actual values and changes from Baseline in quantitative lab values will be summarized by study cohort and timepoint using descriptive statistics. All laboratory values will be classified as normal, below normal, or above normal based on normal ranges supplied by the laboratory. An analysis of laboratory values will be based on frequencies of abnormal values and frequencies of clinically significant abnormal values and will be presented in tabular form by cohort. Shift tables will be produced. All data will be presented in listings by cohort along with individual patient listings for those patients with clinically significant abnormal laboratory values. Graphical displays will be presented as appropriate.

## 11.5.6.5. Safety Variable: Asfotase Alfa Anti-drug Antibody

Shift tables will be produced to show changes from Baseline to scheduled visits in the presence or absence of asfotase alfa ADA. For patients with positive antibodies, the titer level will be summarized using descriptive statistics, and the presence or absence of neutralizing antibodies will be summarized using counts and percentages. These analyses will be performed by cohort. Graphical displays will be presented as appropriate.

## 11.5.6.6. Safety Variables: Vital Signs, Physical Examinations, Renal Ultrasounds, and Ophthalmology Assessments

Actual values and changes from Baseline in vital signs (blood pressure, heart rate, respiratory rate, and temperature) will be summarized by cohort and timepoint using descriptive statistics. Physical examination (including weight), renal ultrasound, and ophthalmology findings will be summarized by cohort and timepoint using counts and percentages. Listings of abnormal results will be provided.

## 11.5.7. Statistical Methods: Study Drug Administration

Study drug administration data will be presented by cohort in a listing.

## 11.5.8. Statistical Methods: Power and Sample Size

A sample size of 9 patients per cohort (27 patients total) will provide sufficient power (>80%) to detect a difference of 2.3 μM between the 9.0 mg/kg/week cohort compared to the 1.5 mg/kg/week cohort, and between the 6.0 mg/kg/week cohort compared to the 1.5 mg/kg/week cohort in the change from Baseline to pre-3rd dose in Week 9 PPi (assuming a SD of 1.5 μM). This is based upon the use of a 2-sided, 2-sample t-test analyzed using a fixed sequence testing procedure with the comparison of the 9.0 mg/kg/week cohort compared to the 1.5 mg/kg/week cohort being performed first, and the hypothesis testing for the second comparison 6.0 mg/kg/week cohort compared to the 1.5 mg/kg/week cohort only being performed if the null hypothesis is rejected for the previous comparison at a significance level of 0.05.

A sample size of 6 patients per cohort (18 patients total) will provide sufficient power (>90%) to detect a difference of 3.2  $\mu$ M (SD 1.5  $\mu$ M) using the same assumptions and fixed sequence testing procedure. A difference of 3.2  $\mu$ M (SD 1.5  $\mu$ M) was observed in adult pediatric-onset treated patients versus controls in Study ENB-009-10 for the change from baseline to Week 6 in

PPi. Between 6 and 9 patients per cohort (18 and 27 patients total) will give sufficient power to detect a mean difference of 2.3 to 3.2  $\mu$ M (SD 1.5  $\mu$ M).

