#### **Statistical methods:**

All data collected in this study will be documented using summary tables, figures, and data listings. For categorical variables, frequencies and percentages will be presented. For continuous variables, descriptive statistics (n, mean, median, standard deviation [SD], minimum, and maximum) will be presented. Descriptive statistics for PK parameters will include the number of observations, mean, SD, coefficient of variation (CV), median, minimum, maximum, geometric mean, and geometric %CV.

Efficacy analyses will be conducted on the Full Analysis Set (FAS), consisting of all treated patients with a predose and at least 1 post-dose PPi level. Safety analyses will be conducted on the Safety Set, consisting of all patients who received at least 1 dose of asfotase alfa. Pharmacokinetic analyses will be conducted on the PK Population, consisting of all treated patients for whom the PK profile can be adequately characterized.

A sample size of 9 patients per cohort (27 patients total) will provide sufficient power (>80%) to detect a difference of 2.3  $\mu$ M between cohorts in the change from Baseline to pre-3rd dose in Week 9 PPi, assuming a SD of 1.5  $\mu$ M and 2-sided, 2-sample t-test analyzed using a fixed sequence testing procedure. A sample size of 6 patients per cohort (18 patients total) will provide sufficient power (>90%) to detect a difference of 3.2  $\mu$ M using the same assumptions. A mean difference of 3.2  $\mu$ M (SD 1.5  $\mu$ M) was observed in adult pediatric-onset treated patients versus controls in Study ENB-009-10 for the change from Baseline to Week 6 in PPi. Between 6 and 9 patients per cohort (18 and 27 patients total) will give sufficient power to detect a mean difference of 2.3 to 3.2  $\mu$ M (SD 1.5  $\mu$ M).

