#### Efficacy/Pharmacodynamics:

The primary endpoint, PPi change from Baseline to pre-3rd dose in Week 9, will be analyzed using a Wilcoxon rank-sum test. A fixed sequence testing procedure will be performed with the comparison of the 9.0 mg/kg/week cohort compared to the 1.5 mg/kg/week cohort being performed first, and the hypothesis testing for the second comparison 6.0 mg/kg/week cohort compared to the 1.5 mg/kg/week cohort only being performed if the null hypothesis is rejected for the previous comparison at a significance level of 0.05. The primary endpoint will be met if the null hypothesis is rejected for both comparisons at a significance level of 0.05. Additionally, the shift

in the distributions and 95% confidence interval (CI) for the above comparisons will be reported using the Hodges-Lehmann-Sen estimate and the exact confidence limits reported.

As secondary analyses, descriptive statistics for the absolute levels and the change from Baseline in PPi will be summarized at all study timepoints by cohort. Within cohort, the change from Baseline to all study timepoints will be analyzed using the Wilcoxon signed-rank test.

Finally, a restricted maximum likelihood (REML)-based repeated measures mixed model will be fitted to estimate the change from Baseline in PPi at each pre-dose timepoint and test whether the change differs from zero at each timepoint. The analysis will include the fixed, categorical effect of visit. The estimate of change from Baseline at defined visits will be provided, along with 95% CIs and p-values. The treatment effect will also be explored.

For the secondary endpoint, change from Baseline to pre-3rd dose in Week 9 in PLP, similar methods as for PPi will be used for analysis.

Individual and mean (±SD) plasma PPi and PLP concentration versus time data will be presented graphically by cohort. Additional analysis of the PD data may be performed if considered useful.

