# 6.1. Overall Study Design

Approximately 27 patients who have provided written informed consent, and have met all the inclusion criteria and none of the exclusion criteria, will be enrolled in the study, with the aim of having at least 6 patients in each cohort completing the study.

Patients will be seen for a Screening visit and will be evaluated after the patient (or legal guardian) provides written informed consent. The Screening visit will include assessments to confirm the diagnosis of HPP, including medical history to confirm onset of HPP symptoms prior to age 18. Patients who fail any of the eligibility criteria may be re-screened only after discussion with the Medical Monitor.

After completion of the Screening visit, patients who meet inclusion/exclusion criteria for Study AA-HPP-208 will be randomized in a 1:1:1 ratio to 1 of the following 3 cohorts:

- **Cohort 1:** Asfotase alfa 0.5 mg/kg initial single dose; followed by multiple dosing starting after 2 weeks at 0.5 mg/kg 3 times per week
- **Cohort 2:** Asfotase alfa 2.0 mg/kg initial single dose; followed by multiple dosing starting after 2 weeks at 2.0 mg/kg 3 times per week
- **Cohort 3:** As fotase alfa 3.0 mg/kg initial single dose; followed by multiple dosing starting after 2 weeks at 3.0 mg/kg 3 times per week

Randomization will be stratified by gender to ensure a similar distribution of gender in each cohort.

Patients will receive a single dose on Week 1, Day 1; on Week 3, Day 1 (Study Day 15) patients will start multiple dosing with the 3 times per week regimen as described above. All doses will be administered as subcutaneous (SC) injections throughout the study.

[figure not shown]

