## 11.5.4. Efficacy/Pharmacodynamic Analyses

## 11.5.4.1. Primary Efficacy/Pharmacodynamic Endpoint

The primary efficacy/PD endpoint will be the change from PPi Baseline to pre-3rd dose Week 9. Baseline is defined as the average of all available Run-in Period assessments on or prior to first SC injection with asfotase alfa. Pre-3rd dose Week 9 is defined as the value obtained prior to the third dose during Week 9. To assess differences between cohorts, the Wilcoxon rank-sum test will be used. A fixed sequence testing procedure will be performed with the comparison of the 9.0 mg/kg/week cohort compared to the 1.5 mg/kg/week cohort being performed first, and the hypothesis testing for the second comparison 6.0 mg/kg/week cohort compared to the 1.5 mg/kg/week cohort only being performed if the null hypothesis is rejected for the previous comparison at a significance level of 0.05. The primary endpoint will be met if the null hypothesis is rejected for both comparisons at a significance level of 0.05. Additionally, the shift in the distributions and 95% confidence interval (CI) for the above comparisons will be reported using the Hodges-Lehmann-Sen estimate and the exact confidence limits reported.

As secondary analyses, descriptive statistics for absolute PPi level and the change from Baseline will be summarized at all study timepoints by cohort. Within cohort, the change from Baseline to all study timepoints will be analyzed using the Wilcoxon signed-rank test.

Additionally, a restricted maximum likelihood (REML)-based repeated measures mixed model will be fit to estimate the change from Baseline in PPi at each pre-dose timepoint during the study period and test whether the change differs from zero at each timepoint. The analysis will include the fixed, categorical effect of visit. An unstructured covariance structure will be used to model the within-patient errors. If this analysis fails to converge, the following structures will be tested and the final covariance structure will be determined by Akaike's information criterion (AIC): first-order autoregressive, compound symmetry, and Toeplitz. The Kenward-Roger approximation will be used to estimate denominator degrees of freedom. The estimate of change from Baseline at defined visits will be provided, along with 95% CIs and p-values. The treatment effect will also be explored.

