#### 7.2.1. Primary Endpoint

The primary endpoint for this study is the change in PPi from Baseline to pre-3rd dose Week 9. Change from Baseline in PPi will be the primary variable. Primary analysis will be performed by using a restricted maximum likelihood (REML)-based repeated measures mixed model, fit for each treatment cohort to estimate the change at each pre-dose (trough) timepoint starting at Week 4 (Day 22) through Week 9 (Day 61). The primary hypotheses will test whether the differences between the cohorts differ from zero at pre-3rd dose Week 9. The Week 3 (Day 15) pre-dose timepoint will not be included in the model assessing change since this is expected to be similar to a baseline level of PPi after the first non-dosing period. The analysis will include the fixed, categorical effect of visit, adjusted for baseline PPi, gender, baseline weight group ( $\geq$  median versus < median), and study drug lot assignment. An unstructured covariance structure will be used to model the within-patient errors. If this analysis fails to converge, the following structures will be tested and the final covariance structure will be determined by Akaike's information criterion (AIC): first-order autoregressive, compound symmetry, and Toeplitz. The Kenward-

Roger approximation will be used to estimate denominator degrees of freedom. The estimated mean change from Baseline at each visit from the model will be provided, along with 95% CIs and p-values.

A fixed sequence testing procedure will be performed with the comparison of the 3.0 mg/kg cohort compared with the 0.5 mg/kg cohort being performed first, and the hypothesis testing for the second comparison 2.0 mg/kg cohort compared with the 0.5 mg/kg cohort only being performed if the null hypothesis is rejected for the previous comparison at a significance level of 0.05 (p-value <0.05). The primary endpoint will be met if the null hypothesis is rejected for both comparisons at a significance level of 0.05 (both p-values <0.05).

The same model will additionally be employed with the fixed, categorical effect of visit, adjusted for baseline PPi.

A similar modeling approach will be employed to explore the effect of treatment cohort on the change from Baseline in PPi at each pre-dose timepoint.

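### The stated power (>80% with 9 per cohort, >90% with 6) holds for one t-test, but the success rule needs two rejections, for which t-test power is about 78% and 85%.

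*Protocol*

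**What the plan says.** Protocol 11.5.8 makes two power statements. The first is "A sample size of 9 patients per cohort (27 patients total) will provide sufficient power (>80%) to detect a difference of 2.3" µM, for the 9.0 versus 1.5 and the 6.0 versus 1.5 mg/kg/week comparisons. The second is "A sample size of 6 patients per cohort (18 patients total) will provide sufficient power (>90%) to detect a difference of 3.2" µM. Both assume SD 1.5 µM. The basis, in the synopsis wording, is a two-sided "2-sample t-test analyzed using a fixed sequence testing procedure". SAP 9.2 carries the same text. None of the three places says whether the percentages refer to one comparison or to both.

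The success rule is explicit in Protocol 11.5.4.1: "The primary endpoint will be met if the null hypothesis is rejected for both comparisons at a significance level of 0.05". The synopsis, SAP 7.2.1 and SAP 7.2.1.4 agree. The 6.0 mg/kg/week comparison is tested only after the 9.0 mg/kg/week comparison has been rejected.

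The planned primary test is not a t-test. Protocol 11.5.4.1 states: "To assess differences between cohorts, the Wilcoxon rank-sum test will be used". SAP 4.1 and 7.2.1 replace this with a REML repeated measures mixed model and make the exact rank-sum test supportive. SAP 9.2 keeps the t-test power text.

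The figure of 6 per cohort matches the completer minimum in Protocol 6.1: "with the aim of having at least 6 patients in each cohort completing the study".

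**The concern.** Fixed-sequence testing spends no alpha on the second test, so the first comparison keeps its full single-test power. The second comparison does not. It can be declared positive only when both tests reject, so its power under the procedure equals the power of the joint event. That is also the power of meeting the primary endpoint.

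The power text names both comparisons and the fixed sequence. A reader may therefore take >80% and >90% as the chance of meeting the endpoint, or of a positive 6.0 mg/kg/week comparison. If the figures are single-test values, both readings are too optimistic. Using a t-test in place of the planned test could add to this at such small sample sizes.

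**Working it through.** **Inputs.** Two-sided 0.05 per comparison (Protocol 11.5). SD 1.5 µM; 9 per cohort with 2.3 µM, or 6 per cohort with 3.2 µM (Protocol 11.5.8). Allocation 1:1:1 (Protocol 6.1). Both higher-dose cohorts are taken to differ from the lowest by the full stated amount, as Protocol 11.5.8 does.

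**Step 1: reproduce the stated figures.** For one two-sample t-test, df = 2n − 2 and the noncentrality is δ / (SD·√(2/n)).

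- n = 9: 2.3 / (1.5 × √(2/9)) = 2.3 / 0.7071 = 3.253, df 16; power 86.3%.
- n = 6: 3.2 / (1.5 × √(2/6)) = 3.2 / 0.8660 = 3.695, df 10; power 91.4%.

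Both stated thresholds hold for one comparison.

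**Step 2: power for both comparisons.** The two contrasts share the 1.5 mg/kg/week cohort, so with equal cohorts their correlation is about 0.5. Joint power therefore lies above the value for independent tests (0.863² = 74.4%; 0.914² = 83.5%) and below single-test power. It was obtained by simulating three normal cohorts, with 1,000,000 replicates per scenario (standard error below 0.05 percentage points).

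**Step 3: the protocol's own test.** The exact two-sided rank-sum test was applied under the same normal assumptions. It rejects at U ≤ 17 or U ≥ 64 for n = 9 (actual alpha 0.0400), and at U ≤ 5 or U ≥ 31 for n = 6 (actual alpha 0.0411).

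| Power, % | One t-test | Both t-tests | Both, variance pooled over three cohorts | One Wilcoxon | Both Wilcoxon |
|---|---|---|---|---|---|
| 9 per cohort, 2.3 µM (stated >80) | 86.3 | 77.6 | 80.0 | 81.4 | 70.5 |
| 6 per cohort, 3.2 µM (stated >90) | 91.4 | 85.4 | 88.6 | 87.3 | 78.9 |
| 7 per cohort, 3.2 µM | 95.5 | 92.1 | not run | 92.2 | 86.7 |
| 9 per cohort, 3.2 µM | 98.9 | 97.9 | not run | 97.9 | 96.1 |

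Repeat simulations agreed to about 0.1 point.

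**Step 4: sensitivity.**

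- Unequal differences (assumed 2.5 and 2.3 µM, 9 per cohort): power for both is 81.2% (t-test) or 74.5% (Wilcoxon).
- Treating the SD as known (normal approximation): 83.5% and 92.7% for both. This meets both thresholds, but it is not the t-test that the text names.
- Closing sentence of Protocol 11.5.8 (6 to 9 patients for 2.3 to 3.2 µM): 6 per cohort with 2.3 µM gives 66.9% for one t-test and 51.9% for both. The sentence is true only if each sample size is paired with its own difference.

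**Step 5: the SAP's mixed model.** Its power cannot be calculated, because the documents give neither a within-patient correlation nor covariate effects.

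**The case against.** The strongest reply is that no stated number is false. The text names a two-sample t-test, the figures are right for that test, and nowhere is >80% or >90% called the probability of meeting the endpoint. On this view the defect is a missing label. That is fair, and the fix is accordingly mainly a label. But the text also places both comparisons under the fixed sequence, and single-test power is not the power of the second comparison there.

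Four further points limit the finding:

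- At 9 per cohort the t-test gap is small. Pooling variance over three cohorts gives 80.0%, and an SD of 1.45 rather than 1.5 µM gives 80.9%. At the 3.2 µM reported from Study ENB-009-10, power for both is 97.9%.
- Six completers need not mean six analysed. The full analysis set requires only one pre-treatment and one on-treatment PPi value. The protocol carries the last observation forward, and the SAP model uses the available troughs. With 7 analysed, t-test power for both at 3.2 µM is 92.1%. The >90% claim is nevertheless made for 6 and should be true for 6.
- The largest gaps concern the rank-sum test, which the SAP has made supportive. They apply to the protocol's primary analysis, not to the SAP's.
- Covariate adjustment could move the power of the SAP's analysis either way. An illustrative ANCOVA with assumed baseline R² from 0 to 0.5 gave about 70% to 95% for both comparisons at n = 9, and 72% to 95% at n = 6. This shows that the t-test figures are not the power of that analysis; it does not rescue them.

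Planning with a t-test as an approximation is ordinary practice, and the actual tests are stated elsewhere. At 6 per cohort, though, the choice of test takes even one comparison below 90%.

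**Conclusion.** The concern holds. The stated power is correct per comparison for a t-test and is not delivered for the plan's own success rule. With t-tests, power for both falls short by 2.4 points at 9 per cohort (80 − 77.6; none with three-cohort pooled variance) and by 4.6 points at 6 per cohort (90 − 85.4; 1.4 with pooled variance). With the protocol's Wilcoxon test the shortfalls are 9.5 and 11.1 points, and >90% at 6 per cohort fails even for one comparison (87.3%).

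These results assume normal data, SD 1.5 µM, equal differences in both higher-dose cohorts and a shared low-dose cohort. A smaller true difference in the 6.0 mg/kg/week cohort would lower power for both further. The misstatement should be corrected, but it affects only how the design's power is described.

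**What to change.** Change the wording in Protocol 11.5.8, the synopsis and SAP 9.2:

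1. Label about 86% (9 per cohort, 2.3 µM) and 91% (6 per cohort, 3.2 µM) as two-sample t-test power for one comparison.
2. Add that t-test power to reject both comparisons is about 78% and 85%, assuming equal differences in both higher-dose cohorts (about 80% and 89% with variance pooled over three cohorts).
3. State that these are t-test figures, not the power of the planned primary analysis. In the protocol and synopsis, name the Wilcoxon rank-sum test and give its power under the same normal assumptions: about 81% and 87% for one comparison, 70.5% and 79% for both. In the SAP, name the REML mixed model and say that its power was not calculated.
4. Optionally, reword the closing sentence to pair 9 per cohort with 2.3 µM and 6 per cohort with 3.2 µM.

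The cost is an edit in three places and less favourable figures. Enrolment, endpoint and test order stay as they are.

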#### 7. STUDY POPULATION

#### 7.1. Inclusion Criteria

Patients must meet all of the following inclusion criteria to be eligible for participation in this study:

- 1. Patients or their legal representative(s) must provide written informed consent prior to undergoing any study-related procedures
- 2. Patient has pediatric-onset HPP, defined as onset of first sign(s)/symptom(s) of HPP prior to 18 years of age
- 3. Patients must have a documented diagnosis of HPP as indicated by a documented history of HPP-related skeletal abnormalities and 1 or more of the following:
  - Documented TNSALP gene mutation(s) from a certified laboratory
  - Serum ALP level below the age-adjusted normal range AND plasma PLP above the upper limit of normal at Screening.

NOTE: Historical results from a certified laboratory for PLP may be used to determine patient eligibility. The criterion for plasma PLP is not applicable if the patient is receiving pyridoxine treatment.

- 4. Patients must have a plasma PPi level of ≥3.9 μM at Screening
- 5. Patients must be  $\geq$ 18 years of age at Screening
- 6. Sexually active male and female patients of childbearing potential must agree to use a highly effective method of birth control during the study and for 3 months following the last dose of study drug. Male patients must also not donate sperm during the Screening and treatment periods and for at least 3 months after the last dose of asfotase alfa. Highly effective contraceptive methods are as follows:
  - a. Combined (estrogen and progestogen containing) hormonal contraception associated with inhibition of ovulation:
    - Oral
    - Intravaginal
    - Transdermal
  - b. Progestogen-only hormonal contraception associated with inhibition of ovulation:
    - Oral
    - Injectable
    - Implantable
  - c. Intrauterine device
  - d. Intrauterine hormone-releasing system
  - e. Bilateral tubal occlusion

- f. Vasectomy with documented medical assessment of surgical success
- g. Condom and spermicide
- 7. Female patients of childbearing potential must have a negative pregnancy test at the time of enrollment
- 8. Female patients not of child-bearing potential due to surgical sterilization (at least 6 weeks after surgical bilateral oophorectomy with or without hysterectomy or at least 6 weeks after tubal ligation) confirmed by medical history, or menopause
  - a. Menopausal women include women with either

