## 11.5. Statistical Methods

All data collected in this study will be documented using summary tables, figures, and patient data listings. For categorical variables, frequencies and percentages will be presented for each cohort and for the combined cohorts (where appropriate). For continuous variables, descriptive statistics (n, mean, median, standard deviation [SD], minimum, maximum) will be presented for each cohort and for the combined cohorts (where appropriate). Descriptive statistics for PK parameters will include the number of observations, mean, SD, coefficient of variation (CV), median, minimum, maximum, geometric mean, and geometric %CV. All hypothesis testing will be 2-sided and performed at the 0.05 level of significance.

Pharmacodynamic/efficacy analyses will be conducted on the FAS, consisting of all treated patients with at least 1 pre-treatment and 1 on-treatment PPi value. Additionally, PD/efficacy analyses will be conducted on the PP Set. Pharmacokinetic analyses will be conducted on the PK population, consisting of all treated patients for whom the PK profile can be adequately characterized. Safety analyses will be conducted on the Safety Set, consisting of all patients who received at least 1 dose of asfotase alfa.

For the PD/efficacy analyses, patients will be considered to be in the treatment cohort to which they were randomized. For safety and PK analyses, patients will be considered to be in the treatment cohort of the treatment they actually received.

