#### Medications and Therapies:

Concomitant medications/therapies are any events with administration dates and times on or after the date and time of the first study drug dose. If the start date of a medication or therapy is partially or completely missing and the end (stop) date and time of the medication/therapy does not indicate that it occurred prior to first dose, then the determination of concomitant status will be based on the following:

If the start year is after the year of the first study drug dose, then the medication/therapy is concomitant; else,

If the start year is the same as the year of the first study drug dose and the start month is missing, then the medication/therapy is concomitant; else if the start month is present and is the same or after the month of the first study drug dose, then the medication/therapy is concomitant; else, if the start date is completely missing, then the medication/therapy is concomitant.

All other medications/therapies are considered prior medications/therapies and could occur from the 30 days prior to informed consent up through the Run-In Period and prior to the 1st dose.

Normal Reference ranges for PPi and PLP:

PPi (μM):	
Male/Female	
13-18 years 0.75-4.78	
>18 years 1-5.82	

PLP (ng/mL):
Male/Female
6-18 years 5.74-61.15
>18 years 2.81-26.70

For observations that fall under the lower limit of quantification (LLOQ), the following values will be used:

Table 4:	Values	Used for	Observat	tions under	the Lower	Limit o	of Q	uantification	(LLOC	))
----------	--------	----------	----------	-------------	-----------	---------	------	---------------	-------	----

Parameter	Value Used
Plasma PPi	0.75µM
Plasma PLP	2.5ng/mL
Serum PTH	.5 x LLOQ

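### The >90% power at 6 per cohort rests on a treated-versus-control difference of 3.2 µM, applied without discount to comparisons between active doses

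*Protocol*

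**What the plan says.** Protocol 11.5.8 makes two power statements, both assuming a "2-sided, 2-sample t-test analyzed using a fixed sequence testing procedure":

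- 9 per cohort (27 in total): power above 80% for a difference of 2.3 µM, "assuming a SD of 1.5" µM. No source is given for 2.3 µM.
- 6 per cohort (18 in total): power above 90% for a difference of 3.2 µM with the same SD. The stated support is that such a difference "was observed in adult pediatric-onset treated patients versus controls in Study ENB-009-10", for the change from baseline to Week 6.

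The section closes by saying that between 6 and 9 per cohort is sufficient for differences of 2.3 to 3.2 µM. The synopsis and SAP 9.2 carry the same figures.

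Protocol 6.1 and 8.1 define three cohorts, all on asfotase alfa, at 0.5, 2.0 and 3.0 mg/kg three times weekly. There is no untreated arm. Under Protocol 11.5.4.1 and SAP 7.2.1 the comparisons are 3.0 against 0.5 mg/kg, then 2.0 against 0.5 mg/kg, on the PPi change to the sample before the third Week 9 dose. The primary endpoint is met only if both reject. Protocol 6.1 aims for at least 6 completers per cohort, and the synopsis lists 18 completers as the minimum.

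**The concern.** The planning difference and the tested difference are different quantities. The earlier figure sets treated patients against controls, whereas this trial sets a higher dose against a lower one. Any PPi reduction on 0.5 mg/kg three times weekly comes off the difference that the test can see, unless the higher doses here lower PPi by correspondingly more than the earlier study's regimen did. Neither document gives that study's doses, an expected PPi change on the low dose, or a discount. The timepoints also differ (Week 6 against Week 9).

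What is exposed is the 6-completer minimum and the closing sentence on 6 to 9 per cohort. The only power statement at 6 per cohort uses 3.2 µM. If attrition brings cohorts down to that size and the low dose is active, a reader would believe the comparison far better powered than it is. A non-significant result could then be misread as absence of a dose response.

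**Working it through.** **Inputs.** SD 1.5 µM; n = 6 or 9 per cohort; differences 3.2 and 2.3 µM (Protocol 11.5.8). For the level, Protocol 11.5 says "All hypothesis testing will be 2-sided and performed at the 0.05 level of significance". The differences 2.4, 2.0 and 1.6 µM are assumptions: 2.4 is 3.2 less 25%, 1.6 is 3.2 less 50%, and 2.0 lies between them.

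**Formula, one comparison.** Two-sample t-test with df = 2n − 2 and noncentrality δ = d / (SD × √(2/n)). Power is the probability that a noncentral t with that df and δ lies beyond ± the 0.975 quantile of the central t.

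**Reproducing the plan.**

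- n = 6, d = 3.2: δ = 3.2 / (1.5 × √(2/6)) = 3.695; df = 10; critical value 2.228; power 91.4%. Stated: above 90%.
- n = 9, d = 2.3: δ = 2.3 / (1.5 × √(2/9)) = 3.253; df = 16; critical value 2.120; power 86.3%. Stated: above 80%.

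Both stated figures are correct for a single comparison.

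**Slack at 6 per cohort.** Solving the same formula for d, 90% power needs at least 3.12 µM and 80% needs at least 2.69 µM. The margin for the 90% claim is 3.2 − 3.12 = 0.08 µM.

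**Power over a range.** Power for both comparisons was simulated, with the 0.5 mg/kg cohort shared and equal true differences assumed for the two higher doses.

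| True difference (µM) | n = 6: one / both | n = 9: one / both |
|---|---|---|
| 3.2 | 91% / 85% | 99% / 98% |
| 2.4 | 71% / 56% | 89% / 82% |
| 2.3 | 67% / 52% | 86% / 78% |
| 2.0 | 55% / 38.5% | 76% / 63% |
| 1.6 | 39% / 23% | 57% / 40% |

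**The closing sentence.** At 6 per cohort, the lower part of the 2.3 to 3.2 µM range, up to 2.69 µM, has less than 80% power even for one comparison. At 2.3 µM it is 67%.

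**The case against.** **The planned size does not rest on 3.2 µM.** The trial randomizes 9 per cohort, powered on 2.3 µM, which is 2.3/3.2 = 72% of the earlier difference. At 2.4 µM, 9 per cohort still gives 89% for one comparison and 82% for both. This stands and confines the point to the 6-per-cohort statement and the closing sentence. It does not supply a source for 2.3 µM.

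**The power sentence is conditional, and the source is disclosed.** The plan says openly that 3.2 µM is treated versus controls, and the arithmetic is right. The closing sentence can also be read as pairing 9 with 2.3 µM and 6 with 3.2 µM, in which case it is correct. That is fair, but the wording does not say so, and the pairing leaves 3.2 µM without support for a dose contrast.

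**Six completers is an aim, not the analysed number.** The plan does not say why six was chosen, and the main objective is PK and PD. Patients who stop early can still contribute, through LOCF in the protocol and available data in the SAP's mixed model. This stands: 6 per cohort is the unfavourable case, not a forecast.

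**Stronger readings that the documents do not support.** A reader might infer that the trial cannot be expected to show 3.2 µM, or that it could do so only if the low dose were inert. Neither follows. The earlier study's doses and the low-dose effect are not given, and higher doses here might do more than the earlier regimen. A reader might also see a ceiling in the PPi scale. Protocol 7.1 says "Patients must have a plasma PPi level of" at least 3.9 µM, and SAP 9.3 substitutes 0.75 µM below the quantification limit, leaving 3.9 − 0.75 = 3.15 µM to fall. But 3.9 µM is a minimum at Screening, while Baseline averages five later samples. A limit for one patient at the threshold does not cap a cohort mean.

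**Conclusion.** The point holds in limited form. The 3.2 µM comes from a different contrast at a different week and is carried over without adjustment, so the claim of more than 90% power at 6 per cohort lacks support for the comparisons this trial makes. If the low dose supplied 25% of a 3.2 µM effect, and the higher doses supplied exactly the whole of it, power at 6 per cohort would be 71% for one comparison and 56% for both. At a 50% share it would be 39% and 23%.

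These are illustrations over assumed differences, not estimates of the low-dose effect. They rest on SD 1.5 µM, normal data and, for the joint figures, equal effects at the two higher doses. They are t-test powers. The SAP's primary analysis is now a covariate-adjusted mixed model, whose power the documents do not give.

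The consequence is for the stated justification and for interpretation should cohorts fall to 6. Type I error and the analysis itself are unaffected.

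**What to change.** In Protocol 11.5.8, the synopsis and SAP 9.2:

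1. Stop using the treated-versus-control 3.2 µM as support for 6 per cohort.
2. State the basis for 2.3 µM as a dose-versus-dose difference, including the PPi change expected on 0.5 mg/kg three times weekly. If no basis exists, say that it is an assumption.
3. Replace the closing sentence on 6 to 9 per cohort with a table of power at 6 and 9 per cohort for differences of 1.6, 2.0, 2.3, 2.4 and 3.2 µM, for one comparison and for both.
4. Say that these are t-test powers, not powers for the SAP's mixed model, and that the joint figures assume equal effects at the two higher doses.

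The cost is a wording change and a less favourable stated power. No patients are added, and neither the design nor the analysis changes.
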